3.1. Study Rationale

This first time in human (FTIH) study intends to identify doses of GSK3358699 that are well tolerated whilst delivering a robust pharmacodynamic response. As such, the study will evaluate the safety, tolerability, pharmacokinetic (PK) and pharmacodynamic (PD) profile of single (in both fed and fasted states) and multiple ascending doses of GSK3358699 in healthy male participants within a pre-defined and controlled pharmacodynamic and pharmacokinetic range for each cohort. Compound exposures

investigated as part of this study will not intentionally exceed pre-defined PK and PD stopping criteria as highlighted in Section 8.

Further, this study will seek to understand the effect of GSK3358699 on systemic markers of inflammation following low dose *in vivo* lipopolysaccharide (LPS) or Granulocyte-Macrophage Colony-Stimulating Factor (GM-CSF) challenge and local inflammation in cantharidin-induced blisters. This experimental approach has been carefully designed to explore the *in vivo* biology of the target and to inform potential immuno-inflammatory indications where GSK3358699 could provide substantial efficacy to address unmet clinical need.

3.2. Background

Pre-clinically, BET inhibitors have demonstrated profound anti-inflammatory and antifibrotic effects, driven by their ability to regulate gene expression at an epigenetic level. Indeed, non-targeted BET inhibitors have been shown to interact *in vitro* with multiple cellular effectors of disease and are efficacious in a range of animal models of disease [Nadeem et al 2015, Meng et al 2014, Cheung et al 2017]. As the first targeted BET inhibitor, GSK3358699 has exhibited potent immuno-modulatory effects *in vitro*, for example in human whole blood assays stimulated with LPS or GM-CSF, as well as in samples from rheumatoid arthritis patients. Further to this, GSK3358699, when investigated in a mouse model of arthritis, effectively inhibited joint inflammation and bone erosion, and abrogated cytokine production in an acute LPS challenge in cynomolgus monkeys. A detailed description of the chemistry, pharmacology and safety of GSK3358699 is provided in the Investigator's Brochure (IB) [GlaxoSmithKline Document Number 2017N333959_00].

3.3. Benefit/Risk Assessment

There is no direct benefit to the participants taking part in this study.

The risk assessment of GSK3358699 is based on the pre-clinical studies conducted to date. Summaries of findings from these pre-clinical studies can be found in the IB. Details of these risks, as well as the risks associated with the challenge agents, and the proposed strategy to mitigate/monitor these risks are detailed in Section 3.3.1. For transparency, emerging clinical data from this study on NSVTs is also included as a potential risk, although causality with GSK3358699 has not been established and similar findings were not observed preclinically.

In this study, safety will be monitored closely both by subjective reporting and by objective means, i.e. serial assessments of vital signs, clinical laboratory information and cardiac monitoring. The study will be run in a clinical unit with immediate access to hospital facilities for the treatment of medical emergencies. Participants will remain monitored in the clinic for the duration of each treatment Period and will only be discharged from the unit at the end of each treatment Period if the investigator deems it safe to do so.

More detailed information about the known and expected benefits and risks and reasonably expected adverse events may be found in the Participant Information Leaflet for GM-CSF and cantharidin and in previous literature for LPS [Fullerton et al 2016].

3.3.1. Risk Assessment

Potential Risk of Clinical Significance	Summary of Data / Rationale for Risk	Mitigation Strategy
	Investigational Medicinal Product (IMP) GSK3358	699
Lipid elevations	 Non-adverse increased triglyceride was evident in female monkeys given ≥ 1 mg/kg/day. Higher triglyceride and/or cholesterol concentrations were also seen in rats given ≥10 mg/kg/day. The effects on triglycerides in monkeys and rats and the no observed effect level (NOEL) for rats are below the maximum predicted human exposure (AUC) at 45 mg. 	 Participant Selection / Monitoring / Stopping criteria: Specific eligibility and withdrawal criteria (see Section 6.2 and Section 8). The protocol includes laboratory assessments for triglycerides. Fasting lipids will additionally be monitored during part C (repeat dosing) of the study. Relevant lipid data from the current and any previous cohort will be considered as part of dose escalation decisions.
Coagulation	 Non-adverse increases in anticoagulant (prothrombin time (PT) and activated partial thromboplastin time (APTT)) and procoagulant (fibrinogen) factors were evident in rats at ≥ 10 mg/kg/day and in individual monkeys given ≥ 10 mg/kg/day in a dose ranging study for 15 days. No changes in PT or APTT were seen in monkeys given GSK3358699 for 6 weeks. The effects on fibrinogen and the NOEL for clotting times in rat are below the maximum predicted human exposure (AUC) at 45 mg. 	 Participant Selection / Monitoring / Stopping criteria: Specific eligibility criteria based on history of prior thrombotic or bleeding disease (see Section 6.2). The protocol includes evaluation of clotting parameters to assess potential changes in fibrinogen, PT and APTT. Relevant coagulation and thrombotic safety data from the current and any previous cohort will be considered as part of dose escalation decisions.
Kidney function	 Non-adverse increased urinary glucose concentration was seen in female monkeys and rats given ≥10 mg/kg/day. Other clinical pathology that may be related to perturbations in kidney function were seen in monkeys or rats. Monkeys given ≥3 mg/kg/day for 6 weeks had decreased plasma albumin; rats given ≥10 mg/kg/day for 6 weeks had decreased urinary volume, lower urinary total protein and protein concentrations, variable changes in plasma creatinine concentration and urea, higher glucose and phosphorus concentrations and slightly lower sodium, 	 Participant Selection / Monitoring/ Stopping Criteria: Specific eligibility - criteria (see Section 6.2). The protocol includes laboratory assessments for renal function, electrolytes, fasting glucose, as well as urinary glucose assessment. Relevant renal and glycaemic safety data from the current and any previous cohort will be considered as part of dose escalation decisions.

Potential Risk of Clinical Significance	Summary of Data / Rationale for Risk	Mitigation Strategy
	 potassium and chloride concentrations. No histological changes were seen in the kidneys of monkeys given GSK3358699. Tubular dilatation and higher kidney weight was evident at the non-tolerated 100 mg/kg/day dose in male rats. Some of the urinary effects in rats are evident below the maximum predicted human exposure (AUC) at 45 mg and the NOEL in monkeys at or below parity to the maximum predicted human exposure (AUC) at 45 mg. 	
Gastrointestinal (GI)	 Gastrointestinal toxicity was observed following repeat oral dosing in rats and cynomolgus monkeys at ≥100 and ≥10 mg/kg/day, respectively. In rats and monkeys there is an approximately 6-fold margin from the maximum predicted human exposure (AUC) at 45 mg to the no observed adverse effect limit (NOAEL) for gastrointestinal effects in the 6 week studies. No gastrointestinal effects were observed in the predicted clinical range up to a maximum of 45 mg. Clinical presentation included body weight reductions and/or loose feces, emesis and reduced food consumption and were dose limiting at ≥100 mg/kg in rats and 30 mg/kg in monkeys. Effects in monkeys dosed for 6 weeks were limited to non-adverse slight erosion, oedema, haemorrhage and inflammatory cell infiltrate in the stomach of a single animal given 10 mg/kg/day. Similar findings, extending to the intestines, were seen in a different study where monkeys were dosed at ≥10 mg/kg for up to 15 days. Effects seen at 30 mg/kg/day for up to 15 days were of greater severity, extended to the intestines and contributed to the morbidity of a single animal. Effects in rats dosed up to 6 weeks included atrophy and ulceration and were considered adverse. 	 Dose Selection: Doses administered as part of this study will not intentionally exceed the GSK3358699 area under the concentration – time curve (AUC) of 255 ng/ml.h, systemic maximum concentration (Cmax)42 ng/ml which are the predicted AUC and Cmax at 45 mg once daily (QD). Participant Selection / Monitoring / Stopping Criteria: Specific eligibility and withdrawal criteria (see Section 6.2 and Section 8) are included. Participant monitoring will be based on prior clinical experience with inhibitors from this target class, Medical history, physical examination and AE reporting will be used to monitor for toxicity in the GI tract. Supportive therapy will be provided as per standard medical practice. In the event of clinically significant toxicity, the participant will be withdrawn and supportive therapy provided according to standard medical practice. Relevant GI safety data from the current and any previous cohort will be considered as part of dose escalation decisions.

Potential Risk of Clinical Significance	Summary of Data / Rationale for Risk	Mitigation Strategy
QTc prolongation	 QTc prolongation was observed in cynomolgus monkeys following single and repeat doses of ≥ 10 mg/kg, up to a maximum of 38 msec increase (16% change from pretreatment), but importantly, no arrhythmias were observed. There is a 3 fold margin and approximate parity to the maximum predicted human exposure (free C_{max} and AUC respectively) at 45 mg to the NOEL for QTc prolongation in monkeys. The QTc prolongation was not induced by direct inhibition of hERG binding with a > 164 fold from the hERG binding inhibitory concentration (IC)50 (89.97 µM) to the GSK3358699 free maximum plasma concentration (C_{max}) at 10 mg/kg in monkeys. 	 Dose Selection: Doses administered as part of this study will not intentionally exceed the GSK3358699 AUC of 255 ng/ml.h, Cmax 42 ng/ml which are the predicted AUC and Cmax at 45 mg QD. Participant Selection/ Monitoring / Stopping Criteria: Specific eligibility and withdrawal criteria (see Section 6.2 and Section 8). The protocol includes cardiac monitoring (12 lead ECGs and telemetry) of participants at each dose level investigated. Relevant cardiovascular safety data from the current and any previous cohort will be considered as part of dose escalation decisions.
Phototoxicity	The ultraviolet (UV)/visible (VIS) spectrum for GSK3358699 showed absorbance in the region of concern which indicate a potential for a human phototoxicity risk.	 Participant Selection / Monitoring: Participants will be advised not to sunbathe or use sunbeds and to wear suitable clothing that minimises exposed areas of skin and to use a broad spectrum UVA/UVB sunscreen and lip balm (SPF ≥ 30) on exposed areas when outdoors. In addition, participants should wear sunglasses that filter UVA and UVB rays. These protections are recommended from day-1 for a minimum of 5 half-lives after GSK3358699 discontinuation. Specific eligibility criteria (see Section 6.2) Physical examination and AE reporting will be used to identify and assess phototoxicity. Relevant safety data from the current and any previous cohort will be considered as part of dose escalation decisions.

Potential Risk of Clinical Significance	Summary of Data / Rationale for Risk	Mitigation Strategy
Testicular	 No testicular findings were observed in monkeys dosed up to 6 weeks at the maximum tolerated dose of 10 mg/kg/day. In the rat, testicular findings (sperm retention and/or minimal to slight germ cell degeneration, tubular vacuolation and multinucleate germ cells) were evident at non-tolerated doses of ≥100 mg/kg/day with an 8-fold margin from the maximum predicted human exposure (AUC) at 45 mg to the NOAEL for testicular effects. 	 Dose Selection: Doses administered as part of this study will not intentionally exceed the GSK3358699 AUC of 255 ng/ml.h, Cmax 42 ng/ml which are the predicted AUC and Cmax at 45 mg QD. Participant Selection / Monitoring: AE reporting will be used to identify and assess any signs and symptoms related to testicular safety. Appropriate contraceptive measures for participants is included in Section 6.1 and Section 12.5. Relevant safety data from the current and any previous cohort will be considered as part of dose escalation decisions.
Aneugenicity	 GSK3358699 has been determined to be an aneugen with a 7fold margin to the maximum predicted human exposure (C_{max}) at 45 mg to the NOEL for aneugenicity in rats. GSK3359699 is derived from a series of benzimidazoles. Benzimidazoles as a class are known aneugens and the rodent carcinogenicity data and clinical exposure data for benzimidazoles indicates that there is no evidence for translation of the observed aneuploidy in to a carcinogenic risk for humans. 	Dose Selection: • Doses administered as part of this study will not intentionally exceed the GSK3358699 AUC of 255 ng/ml.h, C _{max} 42 ng/ml which are the predicted AUC and C _{max} at 45 mg QD.
Haematologic	 Variable changes in red blood cell parameters were noted at non-tolerated doses in both rats and monkeys. At tolerated doses, no hematological changes were seen in monkey and increased red cell distribution width (RDW), reticulocytes and/or MCV were seen in rats. No microscopic changes were observed in the hematopoietic and lymphoid organs of monkeys and those evident in rats given ≥ 100 mg/kg/day were considered 	 Dose Selection: Doses administered as part of this study will not intentionally exceed the GSK3358699 AUC of 255 ng/ml.h, Cmax 42 ng/ml which are the predicted AUC and Cmax at 45 mg QD. Participant Selection / Monitoring / Stopping Criteria: Specific eligibility and withdrawal criteria (see Section 6.2

Potential Risk of Clinical Significance	Summary of Data / Rationale for Risk	Mitigation Strategy
	 non-adverse. Further details are in the IB Section 2. Decreases in platelet count were not observed preclinically with GSK3358699 but have been observed with panBET inhibitors in the clinic. 	 and Section 8). The protocol includes laboratory haematological assessments. Relevant haematological safety data from the current and any previous cohort will be considered as part of dose escalation decisions.
Hepatic	 Findings in the liver of monkeys dosed for 6 weeks consisted of non-adverse centrilobular vacuolation in a single animal given 10 mg/kg/day. Cytoplasmic rarefaction, hepatocellular hypertrophy and microvesicular vacuolation were seen in dose ranging monkey study. Non-adverse effects were also seen in rats given 100 mg/kg/day for 6 weeks and included cytoplasmic vacuolation, cytoplasmic basophilia and decreased inflammatory infiltration. Clinical pathology changes potentially related to the liver findings include higher alkaline phosphatase (ALP) and aspartate aminotransferase (AST) activities in rats given 100 mg/kg/day. Increases in total bilirubin was also evident in rats given 100 mg/kg/day. There was no evidence of hepatobiliary damage in any toxicology studies conducted with GSK3358699. There is approximate parity and a 7- fold margin from the maximum predicted human exposure (AUC) at 45 mg to the NOEL for liver effects in monkeys and rats respectively. 	 Dose Selection: Doses administered as part of this study will not intentionally exceed the GSK3358699 AUC of 255 ng/ml.h, Cmax 42 ng/ml which are the predicted AUC and Cmax at 45 mg QD. Participant Selection / Monitoring / Stopping Criteria: Specific eligibility and withdrawal criteria (see Section 6.2 and Section 8). The protocol includes laboratory liver chemistry assessments. Relevant liver safety data from the current and any previous cohort will be considered as part of dose escalation decisions.
Non-sustained ventricular tachycardia (NSVT)	• Four cases of asymptomatic, non-serious, non-severe and self-limiting NSVT were observed in this study (207546); 2 in Part A and 2 in Part C. There was a lack of correlation between measured GSK3358699 systemic concentrations and the NSVTs. Similar findings were not observed preclinically.	 Participant Selection / Monitoring / Stopping criteria: Specific eligibility criteria (see Section 6.2). Additional withdrawal criterion based on investigator and medical monitor judgement (see Section 8.1.6.). The protocol includes cardiac screening and monitoring (12 lead ECGs and telemetry) of participants at each dose level

2017N332348_05

CONFIDENTIAL

Potential Risk of Clinical Significance	Summary of Data / Rationale for Risk	Mitigation Strategy
		investigated. • Randomisation ratio in Part C has been changed to 1:1
		(GSK3358699:placebo)
		Relevant cardiovascular safety data from the current and any previous cohort will be considered as part of dose escalation decisions.

Potential Risk of Clinical Significance	Summary of Data / Rationale for Risk	Mitigation Strategy
Haemodynamic	 An increase in heart rate (increased by up to 46 beats per minute (bpm)) was observed after 13 doses of a non-tolerated 30 mg/kg/day dose in a single cynomolgus monkey with a 16 fold margin to the NOEL (free Cmax). No abnormalities were observed histologically in the hearts of rats or monkeys given GSK3358699 for up to 6 weeks. 	 Dose Selection: Doses administered as part of this study will not intentionally exceed the GSK3358699 AUC of 255 ng/ml.h, C_{max} 42 ng/ml which are the predicted AUC and C_{max} at 45 mg QD. Participant Monitoring: The protocol includes cardiac monitoring (vital signs, 12 lead ECGs and telemetry) of participants at each dose level investigated. Relevant cardiovascular safety data from the current and any previous cohort will be considered as part of dose escalation decisions.
Drug-Drug Interactions (DDIs)	GSK3358699 is a weak metabolism dependent inhibitor of Cytochrome P450 3A4 (CYP3A4) hence there is a risk of inhibiting CYP3A4 substrate con-meds resulting in clinically relevant DDIs.	 Study Design: GSK3358699 will not be administered with any other drug or known CYP3A4 substrate as part of this FTIH protocol. Human PK data generated as part of this study will be used with in vitro data to inform the DDI risk associated with GSK3358699 and future clinical mitigation strategies.

Potential Risk of Clinical Significance	Summary of Data / Rationale for Risk	Mitigation Strategy
Low-dose LPS, GM-CSF and cantharidin are es	tablished models in healthy volunteer studies and are expected to be section is provided in the interest of full disclosure of all potent	
	Intravenous LPS Challenge Agent	
Immune response leading to influenza – like symptoms.	 Previous studies have shown that single intravenous doses of 0.5 ng/kg (6 EU/ng) has been well tolerated in healthy male participants, however literature reports of 2 ng/kg (10 EU/ng) and above are very poorly tolerated and elicit considerable symptoms. Observed adverse events were of mild severity and self-limiting without therapeutic intervention. 	 LPS will be used at a concentration of 0.75 ng/kg. A low, single dose of LPS is planned which means that systemic exposure will be limited. The participants will be dosed with LPS in a Medicines and Healthcare Products Regulatory Agency (MHRA) accredited clinical research unit and will have regular monitoring of vital signs post dose. Participants will receive telemetry for a minimum of 12 hours post-LPS dose or until their telemetry shows no clinically significant findings for 4 hours (whichever is longer). Participants will be prehydrated with intravenous fluids prior to LPS challenge, and intravenous fluid hydration will continue following the challenge. Normal saline will be infused at a rate of 250ml/hr for 4 hours prior to LPS dosing and 8 hours subsequently. Participants with previous history of frequent vasovagal syncope will be excluded from the study Participants with previous experimental exposure to IV LPS will be excluded.

Potential Risk of Clinical Significance	Summary of Data / Rationale for Risk	Mitigation Strategy		
	Intravenous GM-CSF Challenge Agent			
Risk of respiratory, hepatic, renal and cardiovascular symptoms in addition to fluid retention.	 If used at high doses, GM-CSF administration might result in increased risk of respiratory, hepatic, renal and cardiovascular symptoms in addition to fluid retention; fluid retention findings were observed in patients with cancer in receipt of chemotherapy. 	• GM-CSF will be used at a dose of 60 µg/m ² that has previously been safely explored in a GSK sponsored study conducted in healthy male participants (207654). A low, single dose of GM-CSF is planned which means that systemic exposure will be limited.		
	Observed adverse events were of mild severity and self- limiting without therapeutic intervention.	 Individuals with prior incidence of respiratory or cardiovascular diseases or pre-existing renal or hepatic dysfunction will be excluded from the study. In addition, we will use telemetry for a minimum of 6 hours following dosing, or until normal for 4 hours (whichever is longer). 		
		• Use of healthy volunteers is a mitigation for the fluid retention finding. In addition, a lower, single dose of GM-CSF is planned which means that the AUC and C_{max} will be lower than in the patients in which this was observed.		
	Topical Cantharidin Challenge Agent			
Irritation, burning or toxicity.	Cantharidin is a corrosive chemical substance which when used inappropriately may cause skin irritation, burning or toxicity.	 Cantharidin has been used clinically to treat warts and extensively in a clinical setting in experimental medicine studies to chemically induce blisters. Cantharidin will be used at a known concentration lower than has been safely explored in GSK sponsored studies conducted in patients and healthy participants, (ie reduced in this study from 0.7% to 0.2 %). Participants with a history of lymphangitis and/or lymphoedema or any participant who has undergone surgery resulting in loss of tissue associated with lymphoid drainage (e.g. certain breast surgery procedures) are excluded. Participants will be advised to wear loose clothing at the site of blistering to minimise hyperaesthesia and discomfort that may occur. 		

Potential Risk of Clinical Significance	Summary of Data / Rationale for Risk	Mitigation Strategy
		 For immediate relief of any discomfort, paracetamol, at doses of ≤2 grams/day will be given to the participant, unless, in the opinion of the investigator and sponsor, the medication will interfere with the study.
		• Participants with history of keloids, skin allergy, hypersensitivity, or contact dermatitis, including previous reactions to dressings to be used in this study or any chronic skin disorder (e.g. psoriasis, atopic dermatitis, vitiligo) excepting isolated lesions remote from intended site of application of cantharidin are excluded. Appropriate skin care to avoid dyspigmentation and hypertrophic scar will be implemented.
		• To minimize the risk of infection, appropriate clean procedures will be followed. Participants will be instructed to visually inspect blister sites on a daily basis and are informed what signs of inflammation/infection to watch for and contact the investigator with any concerns.
		• Cantharidin will not be dispensed to participants and all applications will be done at the research centre by suitably trained personnel.

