6.2. Exclusion Criteria

Participants are excluded from the study if any of the following criteria apply:

Medical Conditions

- 1. Current or chronic history of:
 - pancreatitis.
 - diabetes mellitus or impaired glucose tolerance.
 - gastrointestinal disease.
 - liver disease, or known hepatic or biliary abnormalities (with the exception of Gilbert's syndrome or asymptomatic gallstones).

- anaphylaxis, and /or anaphylactoid (resembling anaphylaxis) reactions [Sampson et al 2006].
- renal disease where clinically significant (minor abnormalities may be permitted base on discussion between investigator and medical monitor).
- respiratory disease or conditions including but not limited to asthma, chronic obstructive pulmonary disease (COPD), and bronchiectasis and any current respiratory infection (childhood asthma is not an exclusion criterion).
- sensitivity or severe allergic responses to any of the challenge agents or cantharidin, or components thereof or a history of drug or other allergy that, in the opinion of the Investigator or GSK Medical Monitor, contraindicates their participation.
- frequent vasovagal syncope.
- surgery requiring general anaesthetic or significant trauma in 3 months leading to study enrolment.
- relevant skin conditions (e.g. recent history of eczema or recurrent eczema, keloid, skin allergies, psoriasis, atopic dermatitis, and vitiligo) which in the opinion of the investigator could pose safety issues or cause interference with study procedures.
- sepsis.
- coagulation disorders.
- peripheral oedema, lymphangitis, lymphoedema, pleural or pericardial effusion.
- haemorrhage (eg sub-arachnoid) or hemophilia or a related bleeding disorder.
- 2. History of malignancies e.g. recurrent basal cell carcinoma, haematological malignancy.
- 3. For participants receiving cantharadin: Presence on either forearm of tattoos, naevi, hypertrophic scars, keloids, hyper– or hypo- pigmentation that may, in the opinion of the Investigator, interfere with study assessments. Participants with excessive hair or any skin abnormalities that may, in the opinion of the Investigator, interfere with study assessments.
- 4. History of cardiac disease e.g. congenital heart disease, valvular heart disease, ischemic heart disease, clinically significant atrial or ventricular arrhythmias, QTc prolongation, or cardiac arrest.
- 5. Family history of premature cardiovascular disease, long QT syndrome or sudden death.

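### Protocol Section 3.3.1 relies on exclusions that Section 6.2 contradicts (childhood asthma), omits (lymphoid-drainage surgery) or does not name (prior thrombosis)

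*Protocol*

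**What the plan says.** Protocol Section 3.3.1 lists each risk with its mitigation. Three rows rest partly on who is kept out of the study:

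- **Coagulation (study drug).** The mitigation is "Specific eligibility criteria based on history of prior thrombotic or bleeding disease (see Section 6.2".
- **GM-CSF challenge.** "Individuals with prior incidence of respiratory or cardiovascular diseases or pre-existing renal or hepatic dysfunction will be excluded from the study".
- **Cantharidin challenge.** Those excluded include "any participant who has undergone surgery resulting in loss of tissue associated with lymphoid drainage". The same row excludes a history of keloids and several other skin conditions, with an exception for isolated lesions away from the application site.

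Protocol Section 6.2 is the list that sites apply. Exclusion #1 opens with "Current or chronic history of" and then gives, among others:

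- "coagulation disorders" and, as a separate bullet, "haemorrhage (eg sub-arachnoid) or hemophilia or a related bleeding disorder";
- respiratory disease and "any current respiratory infection (childhood asthma is not an exclusion criterion";
- "renal disease where clinically significant (minor abnormalities may be permitted base on discussion between investigator and medical monitor".

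Section 3.3.3 concludes that the risks are minimal and justified once the protective measures are taken into account. Section 3.3 states that participants gain no direct benefit.

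**The concern.** In a healthy-volunteer study with no benefit to the participant, the benefit-risk conclusion depends on the protective measures being real. Section 3.3.1 describes some of them as firm exclusions, and for coagulation it sends the reader to Section 6.2 to find them.

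If Section 6.2 lacks such a criterion, or says the opposite, a site following the eligibility list correctly can enrol a man whom the risk assessment counts as excluded. The later record would not show it. SAP Section 4.1 builds the inclusion/exclusion deviation listing from the eCRF criteria page, so a man who satisfies Section 6.2 but not Section 3.3.1 generates no entry.

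**Working it through.** No arithmetic bears on the mismatch itself. The check sets each exclusion claimed in Section 3.3.1 against Sections 6.1 and 6.2.

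**Main items**

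1. *Prior respiratory disease (GM-CSF row).* Section 3.3.1 excludes prior disease without exception. Section 6.2 #1 lists asthma and other respiratory conditions but expressly lets childhood asthma through. A man with resolved childhood asthma is out under one section and not excluded under the other. **Direct contradiction**, in a row whose first named risk is respiratory.
2. *Surgery with loss of lymphoid-drainage tissue (cantharidin row).* Section 6.2 #1 names lymphangitis and lymphoedema. Its only surgery criterion concerns general anaesthesia or major trauma in the 3 months before enrolment. **Absent.**
3. *Prior thrombosis (coagulation row).* Bleeding has its own bullet in Section 6.2; thrombosis has none. The nearest term is coagulation disorders, which may cover some thrombotic disease. The stem of #1 requires a current or chronic history, whereas #2 (malignancy) and #4 (cardiac disease) ask for any history. A single resolved clot is arguably neither current nor chronic. **Not named; at best partly covered.**

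**Lesser differences**

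4. *Renal.* Section 3.3.1 excludes pre-existing dysfunction. Section 6.2 excludes clinically significant disease and allows minor abnormalities after discussion. The sections can differ only at the minor end.
5. *Cardiovascular.* Section 3.3.1 speaks of cardiovascular disease. Section 6.2 #4 covers cardiac disease and #5 a family history of premature cardiovascular disease. No criterion names a personal history of non-cardiac vascular disease.
6. *Keloid and skin.* Section 6.2 names keloid in #1 and again in #3 for cantharidin recipients, each time subject to investigator opinion. The difference is a firm rule against a discretionary one.

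**Scope, in planned places (Protocol Sections 5.1 and 5.2)**

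- Coagulation row, everyone who may receive the study drug: 2×9 (Part A) + 6 (Part B) + 14 (Cohort 4) + 3×18 (Cohorts 5-7) + 20 (Cohort 8) = 112.
- GM-CSF row: 9 (Part A Period 4, Cohort 2) + 7 (Cohort 4) + 10 (Cohort 8) = 26.
- Cantharidin row: 18 (Part A Period 4) + 14 (Cohort 4) + 20 (Cohort 8) = 52.

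These are places, not distinct men, because replacement and re-enrolment are allowed. SAP Section 2.3 says that nobody was dosed in Part B and that only Cohorts 4 and 5 of Part C were dosed. For the cohorts that opened, the planned places are 18 + 14 + 18 = 50, 9 + 7 = 16 and 18 + 14 = 32 respectively. Cohort 4 was halted before completion, so the documents do not show how many of its men were challenged. They also do not say how many men had any of these histories.

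**The case against.** The strongest reply is that Section 6.2 does not stand alone. Inclusion #2 requires men to be overtly healthy on medical evaluation, and exclusion #9 lets the investigator decline anyone for whom participation would be unwise. Section 6.4 makes a repeated out-of-range safety test judged clinically significant a screen failure. The bar on waivers in Section 6 does not limit any of this. This stands against any claim that the men concerned are simply eligible; they are only not excluded by a specific criterion. It does not close the gap, because Section 3.3.1 promises exclusion and, for coagulation, specific criteria. For childhood asthma, Section 6.2 tells the site that it is not a reason to exclude.

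Other points on that side also carry weight:

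- *Thrombosis.* Coagulation disorders are listed separately from bleeding, so the term can reach further, and ischaemic heart disease falls under #4. This is a gap in wording, not a contradiction.
- *Lymphatic surgery.* The example given is breast surgery, in an all-male study, and surgery for cancer would usually meet #2. The remaining group is narrow.
- *Renal.* A minor abnormality need not be dysfunction, creatinine is on the clinical chemistry panel, and Section 3.3.1 never claims a creatinine limit.
- *Keloid.* It is in Section 6.2 twice, Section 3.3.1 has its own remote-lesion exception, and sensitivity to cantharidin is a separate exclusion.
- *Severity of the hazards.* Section 3.3.1 calls the coagulation findings non-adverse and reports no change in clotting times in monkeys over 6 weeks. It ties the GM-CSF risks to high doses, while this study plans a low single dose.

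**Conclusion.** The mismatch is real and should be corrected. Of the exclusions claimed in Section 3.3.1, one is contradicted by Section 6.2 (childhood asthma), one is absent (lymphoid-drainage surgery) and one is not named and at best partly covered (prior thrombosis). Renal, cardiovascular and skin history differ in firmness or breadth only. The thrombosis gap reaches every cohort given the study drug; the others matter mainly for challenge participants.

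A reader might infer more, and the documents do not support it:

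- That all the named exclusions are missing and the men are therefore eligible. Keloid and clinically significant renal disease are in Section 6.2, and investigator discretion remains.
- That the drug lengthened clotting times at exposures below the predicted human maximum. Section 3.3.1 places the fibrinogen effects, and the rat no-effect level for clotting times, below the predicted exposure at 45 mg. It does not say that clotting times rose there.

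The conclusion assumes that sites enrol from Section 6.2 as written, and it reads coagulation disorders and the stem of #1 in their ordinary sense. A broad reading of either would shrink the thrombosis item but not the other two. No sample size, endpoint or analysis is affected.

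**What to change.** Reconcile the coagulation, GM-CSF and cantharidin rows of Section 3.3.1 with Section 6.2 line by line, so that both state the same exclusions for the same participants. For each item the sponsor decides whether the criterion or the mitigation claim changes. The conclusion in Section 3.3.3 should then be re-confirmed on the exclusions that actually operate.

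Because the study ended early, the study report should describe the exclusions applied in practice. The sponsor can check the screening histories of the men dosed in Part A and Cohorts 4 and 5 against the claims in Section 3.3.1. The SAP's display list shows medical conditions only for subjects with liver stopping events, so that check has to use the screening record.

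The cost is a few lines of text, using medical history already taken. The downside is slightly fewer eligible volunteers if criteria are tightened, or a slightly weaker mitigation statement if the claims are corrected.
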